Non-adherence to medications will be assessed by the **Medication Adherence Questionnaire** (**MAQ**) designed to measure medication adherence behaviour and barriers such as forgetfulness, carelessness, adverse effects and efficacy. MAQ includes simple four-item dichotomous questions, scoring one point for each yes response; total scores are categorised as: 0 point indicating high; 1-2 points medium, and 3-4 points low medication adherence behaviour.

The Adherence to Refills and Medications Scale (ARMS) will be used to determine the patient medication adherence behaviour in terms of self-regulation. The ARMS comprises a 12-item scale with the first 8-item medication taking subscale assessing correct self-administration ability for the prescribed regimen. The next 4-item prescription refill subscale assesses the patient's ability to refill medications on schedule. Each item is scored on a four point scale ranging from l=

Version 2: 20/05/2016 ----- Page 15 of 42

none of the time to 4= all the time. The higher numbers on the scale demonstrate patient's better ability to refill medications on schedule.

The Belief about Medicine Questionnaire (BaMQ) elicits information on patients' beliefs about their medicines where they may relate to adherence. It identifies whether the patient holds beliefs that their medicines are necessary or if they have concerns about their medicines. The study will use the short version of the BaMQ (the 8-item) developed by Horne et al., 1999. This version is composed of four subscales containing two items each, and assessing: General Harm; General Overuse; Specific Necessity; and Specific Concerns. Respondents indicate their degree of agreement with each statement on a five point Likert scale, ranging from l=strongly disagree to 5=strongly agree. The lower numbers on the scale demonstrate the patient's strong beliefs about taking medications. Scores are summed to give a total score, with higher scores indicating more positive beliefs. The focus of the BaMQ, is identification of barriers to medication adherence, contributing to comprehensive evaluation of the drivers behind medication adherence.

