Pilot trial phase: The researcher will compare the two groups at baseline. Data will be analysed according to intention to treat analysis using statistical methods based on the study hypothesis. The primary outcome will be medication adherence/non-adherence at six months and changes in adherence scores since baseline. Descriptive statistical analyses will be used to illustrate the participants' baseline characteristics. The independent samples t-test will be used to compare the mean medication adherence questionnaire scores (MSSS, MAQ, ARMS, BaMQ, and MASER-R) between the intervention and usual care groups. Paired samples t-test analysis will be used to test within groups differences on medication adherence questionnaire scores (MSSS, MAQ, ARMS, BaMQ, and MASER-R). Logistic regression analysis will be applied to identify variables that significantly influence adherence to medications (i.e. self-efficacy, beliefs, level of confidence, and social support).

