27. When you feel well				

Version 2: 20/05/2016 ------ Page 30 of 42

28. If they make you want to urinate while away from home				
Please rate how sure you are that you can carry out the following task:				
29. Make taking your medications part of your routine				

Version 2: 20/05/2016 ------ Page 31 of 42

There are no right or wrong answers. For each of the beliefs listed below, please rate how you agree or disagree about your beliefs of taking medications.

Items	Strongl y Agree	Agree	Uncertai n	Disagree	Strongly Disagree
30. My health, at present, depends on my medicines					
31. My medicines protect me from becoming worse					
32. My medicines disrupt my life					
33. I sometimes worry about long-term effects of my medicines					
34. Doctors use too many medicines					
35. People who take medicines should stop their treatment for a while every now and again					
36. Most medicines are addictive					
37. Medicines do more harm than good					

For the next set of questions, please indicate how often people may have helped you in the various ways described during the PAST THREE MONTHS.

How often has someone in the past three months?

Questions	Never	Rarely	Sometime s	Often	Very often
38. Helped you monitor your symptoms and medication side effects?					
39. Reminded you to take your medications?					
40. Picked up your cardiac medication prescriptions for you?					
41. Helped you understand information about your medications?					
42. Checked in with you about your medications?					
43. Encouraged you to talk to your doctor about your medications when you have questions or problems?					
44. Helped you to believe you can take your medications as prescribed?					
45. Called you specifically to ask how you were doing with your cardiac medications?					

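### As written, the BaMQ total sums two items favourable to medicines and six unfavourable ones with no stated reversal, so a broad improvement in beliefs lowers a score the protocol reads as higher-is-better

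*Protocol*

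**What the plan says.** Section 5.3.1 describes the short BaMQ: "This version is composed of four subscales containing two items each, and assessing: General Harm; General Overuse; Specific Necessity; and Specific Concerns". Responses are on a "five point Likert scale, ranging from l=strongly disagree to 5=strongly agree". Two sentences on direction follow. The first is "The lower numbers on the scale demonstrate the patient's strong beliefs about taking medications". The second, which also gives the total rule, is "Scores are summed to give a total score, with higher scores indicating more positive beliefs".

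Appendix A prints the eight statements as items 30 to 37, without subscale labels and with the strongest agreement as the first response column. Two statements favour medicines: "My health, at present, depends on my medicines" (item 30) and "My medicines protect me from becoming worse" (item 31). The other six express disruption, worry, overprescribing, the wish for treatment breaks, addiction and harm; the last reads "37. Medicines do more harm than good".

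Section 9, pilot trial phase, says "The independent samples t-test will be used to compare the mean medication adherence questionnaire scores" and lists the BaMQ among those scores. It plans paired t-tests within groups on the same list. Section 9, phase one, summarises beliefs by their mean. Neither Section 5.3.1, its instrument table, Appendix A nor Section 9 mentions reverse-coding or separate scoring of the subscales.

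**The concern.** A summed score has a meaningful direction only if every item points the same way once coded. Here one coding applies to all eight statements, yet agreement is the favourable answer on two and the unfavourable answer on six. The unfavourable items dominate a plain sum, so the total runs mainly opposite to the direction the protocol gives it. The earlier sentence about low numbers leaves a reader without a second statement to settle the matter.

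The stake is the interpretation of the BaMQ comparisons. Beliefs are among the things the intervention tries to change: the sample counselling script in Appendix D takes up beliefs about side effects and harm. If counselling reduced such beliefs, the BaMQ total in the intervention arm would fall, and the stated rule would have that reported as less positive beliefs. In phase one, the mean BaMQ score would be misread in the same way.

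**Working it through.** The protocol gives no BaMQ range, expected value or effect, so there is no stated figure to reproduce. The check is score arithmetic on the stated rule.

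**Inputs**
- Coding: 1 = strongly disagree to 5 = strongly agree, all items (Section 5.3.1).
- Items: 8, of which 2 favourable (30, 31) and 6 unfavourable (32 to 37), classified from the statements in Appendix A.
- Rule: total = sum of the eight responses, higher meaning more positive (Section 5.3.1).

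**Total as written** (possible range 8 × 1 = 8 to 8 × 5 = 40)
- Most favourable respondent: 2 × 5 + 6 × 1 = 16.
- Neutral respondent: 8 × 3 = 24.
- Least favourable respondent: 2 × 1 + 6 × 5 = 32.
- The maximum of 40 requires strong agreement with all eight statements, both that medicines protect and that they do more harm than good. It is not the most positive belief.

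**Change in the total as written**
- One-point favourable shift on every item: 2 × (+1) + 6 × (-1) = -4.
- Largest gain on the two favourable items alone: 2 × (5 - 1) = +8.
- Largest improvement on the six unfavourable items alone: 6 × (1 - 5) = -24.
- Cancellation: if the two favourable items each rise by a and the other six each improve by b, the change is 2a - 6b. With a = 3 and b = 1 it is 6 - 6 = 0, so a patient who improves on all eight items shows no change.

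**Total with items 32 to 37 reversed (6 - response)**
- Most favourable: 2 × 5 + 6 × (6 - 1) = 40.
- Neutral: 2 × 3 + 6 × (6 - 3) = 24.
- Least favourable: 2 × 1 + 6 × (6 - 5) = 8.
- One-point favourable shift on every item: 2 + 6 = +8.

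The stated direction is then true over the whole range.

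**Coding by printed column order** (1 = strongly agree to 5 = strongly disagree)
- Most favourable: 2 × 1 + 6 × 5 = 32.
- Least favourable: 2 × 5 + 6 × 1 = 16.

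These extremes are ordered as the protocol says. But this coding contradicts the one in Section 5.3.1, and the two favourable items now count the wrong way. No single coding of all eight items, in either direction, makes the plain sum a coherent measure of positive beliefs.

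**The case against.** The strongest reply is that the protocol is silent on reversal and does not forbid it. It states the intended direction of the total, names a published instrument with defined subscales, and could leave item recoding to a scoring manual or an analysis plan not shown here. That stands as far as it goes: the error belongs to the scoring as written, and the documents do not show that data will be entered that way. It does not remove the point, because the protocol does not leave scoring open. It fixes a coding, a summing rule and a direction, and together these give the wrong answer.

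A reader might also infer more than the documents support:
- **That the sign of every BaMQ result is wrong.** It is not. Even with an unreversed sum, a gain confined to the two favourable items raises the total, by up to 8. Entry in printed column order would give a different sign again.
- **That the two direction sentences flatly contradict each other.** The first may refer to single responses and the second to the total, and strong beliefs are not the same as positive ones. The sentences appear to conflict, but a strict contradiction is only one reading.
- **That the BaMQ total enters the logistic regressions.** Section 9 names beliefs as a variable for the pilot trial regression, and for phase one only factors and behaviours. Neither says whether a total or a subscale is used. The documented uses are the t-tests and the phase one mean.

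Finally, the 16-point gap between extremes (32 - 16) is a theoretical limit. The documents give no expected BaMQ effect, so it is not a forecast of bias.

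**Conclusion.** The concern holds for the scoring as written. With the stated coding and a plain sum, the most favourable respondent scores 16 and the least favourable 32, and uniform improvement by one point per item lowers the total by 4. Broad improvement in beliefs, or improvement in concerns, overuse or harm, would be reported as worsening in the between-group and within-group t-tests, with necessity gains of at most 8 working against it.

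This rests on two assumptions: that items are summed without reversal, since none is stated, and that items 30 and 31 are favourable and 32 to 37 unfavourable, which their wording makes plain.

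It should be fixed, but it does not threaten the trial's design. The BaMQ measures beliefs. The pilot trial's primary outcome is medication adherence (Sections 2.2 and 9), the 9 per group and 28 in total are tied to that outcome, and adherence status for trial entry is assigned from the MAQ (Section 5.4). Item-level responses are kept on paper, so the scoring can be corrected without losing data.

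**What to change.** In Section 5.3.1:
1. State one direction for the total, and remove or reword the sentence about low numbers.
2. Either reverse items 32 to 37 (6 minus the response) before summing, giving a total of 8 to 40 with higher meaning more positive, or analyse the subscales separately. If separately, state which items form each subscale and its direction, because Appendix A does not label them.
3. Give the numeric code for each printed response column. Appendix A puts the strongest agreement first, so left-to-right numbering at data entry would invert the stated coding.

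In Section 9, say which BaMQ score (total or subscale) the t-tests use.

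The cost is a few lines of scoring text, with no new data and no change to the questionnaire or sample size. It should be settled before any BaMQ data are scored.

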#### 5.3.2. Phase two (Qualitative Exploratory semi-structured interview)

**Sample and sampling approach:** Participants for this phase will have already participated in phase one of the study (See phase one). All participants who complete the survey (**Appendix A**) will be eligible to participate in the interview regardless of their survey results (i.e. whether or not the survey indicates they are adherent or non-adherent to their medications).

**Interview schedule**: A schedule of open-ended questions has been developed based on the literature to address the second primary objective of the study; this may be modified by the researcher based on results from phase one (**Appendix C**).

Interview procedure: Consent for this phase of the study will be obtained as the same time when participants give consent to Phase one and will be checked with participants prior to starting the interview. The semi-structured interviews will be conducted during a face to face meeting between the researcher and participants guided by a set of questions (Polit and Beck, 2004). The times and locations of the interviews will be arranged with participants to coincide with their routine visits to cardiac rehabilitation. Interview date and time will be arranged with participants at the visit when the survey is distributed, with a telephone reminder text two days before the scheduled interview.

Interviews will be digitally audio-recorded and transcribed by the researcher for analysis. The researcher will facilitate the discussion and create a comfortable environment. The setting chosen for the interviews will be neutral, comfortable, not intimidating, accessible, and amenable to audiotape recording (Polit and Beck, 2004). One of the meeting rooms at POWH will be used. Participants will be encouraged to talk about their beliefs and attitudes on taking medications as well as perceived barriers and facilitators. The researcher will take notes of the participants' body language and other non-verbal cues. Semi-structured interviews are anticipated to take up to 30-45 minutes. Immediately after each interview, the researcher will debrief participants while the recorder is still running and will label all tapes and notes with the date, time, and participant code.

#### **5.3.3.** PILOT TRIAL PHASE (PHASE THREE)

**Sample and sampling approach**: Patients identified as 'non-adherent', based on the results of exploratory phases (Phase one and Phase two), will be invited to participate in the pilot randomised trial phase.

#### 5.4. RECRUITMENT AND SCREENING

Patients identified as 'non-adherent' to at least one of their cardiac medications based on the result of exploratory phases (Phase One and Phase Two) will be invited to participate in this pilot

Version 2: 20/05/2016 ----- Page 18 of 42

randomised trial phase. Participants will be assessed as adherent or non-adherent based on the response to the Medication Adherence Questionnaire (MAQ). Patient with a total score of 1-2 will be considered as "adherent", and those with a total score of 3-4 as "non-adherent". At conclusion of the interview (Phase Two), eligible participants who are identified as "non-adherent" will be informed about Phase 3, the pilot RCT trial phase.

#### 5.5. INFORMED CONSENT PROCESS

Prior to conducting the research, the researcher will obtain informed and voluntary consent from participants for phases one and two, and separately for the pilot trial phase. All prospective participants will be informed of the study purpose via participant information sheets. The participant information sheets will contain information about the purpose and objectives of the research as well as an explanation of what will be required of a participant during each phase, how research data will be gathered and analysed and what will happen to the information once the research is complete.

The researcher will provide an enrolment folder to the patient including written information about the study, a copy of their consent in addition to face to face explanation of the study. Written consent will then be sought to participate in Phases one and two.

At conclusion of the interview (Phase Two) eligible participants will be informed about phase three, the pilot RCT trial phase. A participant information sheet specific to this phase will be provided to the eligible participants and verbal and written consent will be obtained prior to randomisation for the pilot trial phase. Contact details for the researcher will be provided and prospective participants invited to ask questions about the research during discussions/ the consent process and/or via phone, email or text message if they wish to do so.

#### 5.6. RANDOMISATION PROCEDURE: PILOT TRIAL PHASE ONLY

In pilot trial phase participants will be randomly allocated to receive either multifaceted intervention comprising current standard care plus motivational interviewing (MINT) follow by text messages or current standard care alone. Participants will be randomised after they have consented to participate in the trial phase, so that the decision to participate has no bearing on which arm of the trial they are allocated to. A random sequence will be generated by computerised random number generator and using permutated blocks in order to assure equal numbers in each arm, balanced at set intervals at 1:1 ratio.

Version 2: 20/05/2016 ----- Page 19 of 42

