#### 3.2. STUDY GROUPS

Participants will be cardiac patients referred to a cardiac rehabilitation program following their hospital admission for acute cardiac events; those participating in the pilot trial phase will be randomly allocated to receive either the intervention plus usual care or usual care only.

Version 2: 20/05/2016 ------ Page 9 of 42

**Intervention group:** Participants in the intervention group will receive usual care plus behavioural counselling about medication adherence using MINT techniques and text message reminders. Each patient will receive approximately 30-40 minutes of a single MINT counselling session following recruitment (Appendix D) (Ma et al., 2014). The core of motivational interviewing is for the counsellor to be simultaneously sympathetic and supportive, as well as directive in moving patients toward change by strengthening their own reasons for change (Levensky et al., 2007). As part of the MINT counselling, the researcher has the opportunity to provide information that the patient may need or to explore some of the barriers that keep this patient from adherence to medications (Dart, 2010). Text message reminders (TM) (Appendix E) will be sent to these participants: one text message daily for two weeks, then on alternate days for two weeks and then on a weekly basis for the next 6 months (Wald et al., 2014). The content of the text message reminders will vary according to the patients' non-adherence factors. An example of the text message reminder is:

The researchers will use a structured MINT counselling script (Appendix D) designed for patients with low adherence to medications, with each session tailored to the medication adherence characteristics of the individual patient (Dart, 2010). All MINT sessions will be audio taped and reviewed by a clinician qualified in MINT to ensure fidelity to the technique (Ma et al., 2014).

**Control group**: Patients randomised to the control group will receive standard care alone for the study period. They will be contacted at baseline and 6 months to complete the same measurements and interviews as the intervention group.

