#### 3.4. NUMBER OF CENTRES

The cardiac rehabilitation center at Prince of Wales Hospital (POWH).

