#### **5.3.1.** Phase one (Quantitative Exploratory survey)

**Sample and sampling approach**: The method of consecutive sampling will be used. This technique involves selecting all eligible participants who agree to participate, provided they meet inclusion criteria, until a desired number of participants has been recruited (Schuster and Powers, 2005). The survey sample will be selected as a consecutive cohort of patients referred to cardiac

Version 2: 20/05/2016 ----- Page 14 of 42

rehabilitation for cardiac disease secondary prevention. Cardiac patients eligible to participate will be identified by the Clinical Nurse Consultant in Cardiac Rehabilitation as they attend for their first session of cardiac rehabilitation. Those interested will be referred to the researcher, who will explain the survey (phase one) and the semi-structured interview (phase two) and will provide them with an information statement sheet and consent form. These two study phases will identify patients who are non-adherent with at least one cardiac medication who will be eligible to participate in the pilot trial phase (phase three). The survey and semi structured interviews will also identify factors that impact on the patients' adherence to cardiac medications.

Questionnaire Instrument: The instrument consists of a number of questionnaires to gather data about medication adherence, patient behaviours, beliefs and other factors associated with medication non-adherence (Appendix A). The questionnaires will be paper based, self-administered, simple and easy to complete, and suitable for participants with low literacy skills. Data collected will include demographic data: age, gender, marital status, social background (next of kin/ carer), home domicile situation, level of education, literacy, and ethnicity / country of birth; and clinical data: disease diagnosis and co-morbidities (Appendix B). Medication practices will be explored using the following instruments:

- Medication Adherence Questionnaire (Morisky et al., 1986).
- Adherence to Refills and Medications Scale (Kripalani et al., 2009).
- Belief about Medicine Questionnaire (Horne et al., 1999).
- Medication Adherence Self-Efficacy Scale-Revised (Fernandez et al., 2008).
- Medication Specific Social Support (Lehavot et al., 2011).

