#### 7. BLINDING AND UNBLINDING

Neither participants nor researcher can be blinded to the group allocation of participants (intervention or usual care only groups).

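### Section 5.6 does not secure unpredictability of the next allocation: blocks balanced at set intervals, one site, and an unblinded researcher who also invites, consents and counsels

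*Protocol*

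**What the plan says.** Section 5.6 specifies a computer-generated random sequence "using permutated blocks in order to assure equal numbers in each arm, balanced at set intervals at 1:1 ratio". It places randomisation after trial consent, "so that the decision to participate has no bearing on which arm of the trial they are allocated to". Section 5.5 repeats that order: "verbal and written consent will be obtained prior to randomisation for the pilot trial phase". Section 5.6 gives no block length, no holder of the list and no mechanism for releasing allocations.

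Section 7 states: "Neither participants nor researcher can be blinded to the group allocation of participants". Section 3.4 names one centre.

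The researcher's tasks are spread over several sections:
- Section 5.3.1: the clinical nurse consultant identifies eligible patients, and those interested go to the researcher.
- Section 5.3.2: the researcher conducts the phase two interview.
- Section 5.5: "the researcher will obtain informed and voluntary consent from participants for phases one and two, and separately for the pilot trial phase".
- Section 3.2: the researchers deliver the motivational interviewing.
- Section 9, phase two: if the researcher finds that survey and interview answers conflict, the participant is asked which one counts for trial eligibility.

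Two provisions limit selection. Sampling into phases one and two is consecutive (5.3.1), and non-adherence is defined as a MAQ total of 3-4 (5.4).

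**The concern.** Randomising after consent stops a patient from deciding with knowledge of the arm. It does not stop the person making the invitation from anticipating the arm, because the invitation and any clarification of eligibility come before consent. In permuted blocks each allocation carries information about the next. At a single site, a researcher who delivers the intervention knows who was allocated to it and therefore knows the running balance.

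If that expectation influences, even without intent, how warmly a patient is invited or how a conflicting answer is explored, the arms can differ at entry. Intention-to-treat analysis (section 9) does not correct this, and neither blinding nor an objective outcome stands behind it: the trial is open and adherence is self-reported. Concealed, unpredictable allocation is therefore the main protection for the comparison, and section 5.6 describes none beyond the order of consent.

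**Working it through.** **Inputs.** 1:1 permuted blocks (5.6); 28 participants, 14 per arm (3.3 and 8); planning difference 4.42 points and SD 3.285 (3.3). Block length is an assumption, shown over the range 2 to 14.

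**The plan's own figure.** Section 8: n = 2 × 7.8512 × 10.7912 / 19.5364 = 8.67, so 9 per group. The total of 28 follows as 9 × 1.5 = 13.5, rounded to 14 per arm. Whether that attrition allowance is right is a separate question; 28 is used here only as the number randomised.

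**Two measures of predictability, by enumerating every balanced block.**
- *Certain*: one arm's quota in the block is already full. This requires a fixed and known block length.
- *Best guess*: always name the arm with fewer participants so far, and toss a coin when tied. This requires no knowledge of block length.

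Worked example, blocks of 4. Up to swapping arms the sequences are AABB, ABAB and ABBA, with 2, 1 and 1 certain allocations. The mean is 4/3 per block; 4/3 ÷ 4 = 33%, and over 7 blocks 9.3 of 28. Best-guess success by position is 1/2, 2/3, 2/3 and 1, total 2.833; 2.833 ÷ 4 = 70.8%.

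| Fixed block length | Certain per block | Share certain | Of 28 | Best guess correct |
|---|---|---|---|---|
| 2 | 1 | 50% | 14 | 75% |
| 4 | 1.333 | 33% | 9.3 | 70.8% |
| 6 | 1.5 | 25% | 7 (pro rata) | 68.3% |
| 8 | 1.6 | 20% | 5.6 (pro rata) | 66.6% |
| 14 | 1.75 | 12.5% | 3.5 | 63.5% |
| Simple randomisation | – | 0% | 0 | 50% |

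Lengths 6 and 8 do not divide 28, so their counts are pro rata.

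**Randomly varying lengths.** Sizes are drawn with equal probability, and the observer knows which sizes are possible but not their order. Certain allocations were obtained by simulating 28 participants.
- Sizes 2, 4 and 6: about 1 of 28 certain. Best guess (1.5 + 2.833 + 4.1) / 12 = 70.3%.
- Sizes 4, 6 and 8: under 1 of 28 certain. Best guess (2.833 + 4.1 + 5.329) / 18 = 68.1% over whole blocks, and slightly lower, about 67%, when the last block is cut off at 28.

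Varying the length removes nearly all certainty. It does little for best guessing, and least when blocks of 2 are included.

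**Illustrative bias (assumed).** Take fixed blocks of 4 with the length known, and suppose that every participant entering on a certain allocation is 0.5 SD better or worse in prognosis, in whichever direction favours one arm. The arms then differ by 1/3 × (0.5 + 0.5) = 0.33 SD with no treatment effect. For scale, with 14 per arm:
- Standard error of the difference: √(2/14) = 0.38 SD.
- Difference needed for two-sided p < 0.05: 2.06 × 0.38 = 0.78 SD (t, 26 degrees of freedom).
- Planned effect: 4.42 / 3.285 = 1.35 SD; 0.33 / 1.35 is about a quarter.

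**The case against.** The strongest reply is that the protocol is silent here rather than wrong. The set-interval wording may merely describe what permuted blocks do, and block length and list holder are often kept out of a protocol precisely to protect concealment. A reader might infer that the researcher can foresee allocations. The documents do not show that: a constant length is only the natural reading, certainty also requires the length to be known, and a separately held list is not ruled out.

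A reader might also infer that the independence statement in 5.6 is false. Read literally, it says only that the patient's decision does not bear on the arm, which consent before randomisation supports. It does not claim to cover the recruiter. The fair criticism is that nothing else in the section does.

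Discretion is narrower than it may look. Sampling is consecutive, the nurse consultant identifies patients, the MAQ cut-off is numeric on a self-completed survey, the interview is booked when the survey is handed out, and the participant decides which conflicting answer counts. This leaves limited room to hasten or delay entry. What stays open is how the invitation is made and how conflicts are found and put to the patient.

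Finally, a reader might infer that a few steered patients could create an apparent effect. The illustration does not support this: 0.33 SD is below one standard error and well short of 0.78 SD. Nor are set intervals the whole leak, since varying blocks of 2, 4 and 6 leave best guessing near 70%.

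**Conclusion.** The point holds in a limited form: as described, section 5.6 does not secure unpredictability of the next arm from the person who invites and consents. It rests on reading the set-interval wording as a constant block length and on the counselling researcher in 3.2 being, or sharing information with, the recruiting researcher in 5.5.

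Predictability can be stated only as a range: 12.5% to 50% of allocations certain if the length is fixed and known, and 63% to 75% correct guesses even if it is not. The documents give no basis for the size of any resulting bias. The 0.33 SD figure rests on an assumed 0.5 SD steering of every known allocation; it would distort the estimate but would not by itself yield significance. This is a cheap improvement to make before the first participant is randomised, not evidence that the comparison is invalid.

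**What to change.** Amend section 5.6 in three places:

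1. Have a supervisor not involved in recruitment generate and hold the list (section 11 shows that supervisors are already on the study). Release each allocation only after eligibility is fixed, trial consent is signed and the participant is logged.
2. Replace the set-interval wording with randomly varying block sizes, not disclosed to the researcher and without blocks of 2. The protocol need not print the sizes; 4, 6 and 8 are one example.
3. State that randomising after consent protects against the patient choosing by arm, and that concealment protects against the recruiter's expectation.

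The cost is a few sentences and a little of a supervisor's time. The arms may end a few participants apart if recruitment stops mid-block, and some guessing above chance remains because the researcher still sees past allocations. That residue is why the separate list holder and the release rule matter at least as much as the block sizes.
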